**SUMMARY OF THE PROTOCOL**

**1. Brief description of the protocol, procedures, and table for schedule of events**

This study targets individuals in Chicago who have received naloxone administered by first responders within the past week to reverse an overdose, but who have not entered into MAT. Study participants will be recruited through partnerships with the Chicago Fire Department (CFD) and/or Police Department (CPD); first responders will be trained to seek consent from individuals who are alert and oriented after receiving naloxone for future contacts by research staff as part of the naloxone standard protocol. Those who consent will be contacted and screened for study eligibility ideally within one week of naloxone administration; eligible participants will be randomly assigned either to the control group, i.e., referral to MAT as usual, or to Recovery Initiation and Management after Overdose (RIMO), an assertive linkage and recovery support intervention. This intervention builds on an evidence-based intervention for treatment linkage, monitoring, and recovery support evaluated in 3 prior clinical trials by the study team.

In Phase 1 (R21), the study team worked with the CFD to train Emergency Medical Service (EMS) teams to obtain authorization for release of contact information from individuals after an overdose reversal. The experimental pilot study tested the feasibility of each step in the intervention protocol and compared individuals who were randomly assigned to receive either a treatment referral pamphlet or the RIMO intervention on treatment received at 30-day follow-up. Qualitative data was also obtained from a focus group with participants in the RIMO group. A total of 75 individuals who had received naloxone from EMS were informed about the study; 50 (67%) of these signed the authorization form and provided their contact information; 33 met with the study team, consented to participate, and were randomized. Compared to the control group, the RIMO group (n=16) had higher odds of receiving any treatment for opioid use (OD = 7.94) and any MAT (OR = 20.2); they received significantly more days of opioid treatment (15.2 vs. 3.4) and more days of MAT (11.2 vs. 0.76) relative to the control group (n=17; all p < .05). Qualitative data highlighted the core components of the RIMO intervention. The pilot study demonstrates the feasibility of partnering with EMS and using the RIMO intervention to address the challenges of linking and engaging individuals into MAT after opioid overdose. These findings have been submitted for publication ([name] et al., under review) and were used to refine the study design for phase 2.

In Phase 2 (R33), research staff will continue to work with the CFD's EMS division and CPD to identify people who have just had an opioid overdose reversed with naloxone, recruit them into the trial, randomize them to a passive referral (via a brochure) vs. the RIMO experimental group. Using the study recruitment and RIMO procedures refined in Phase 1, a total of 350 individuals will be recruited and randomly assigned to the "referral to MAT" control or to "RIMO". All participants will receive standardized assessments at baseline and 3, 6, and 9 months post-randomization. The study's aims and their associated hypotheses are:

**Aim 1: Evaluate RIMO's direct effect on linkage to MAT, length of time on MAT, dropout, and total days of MAT.**

H1: Relative to the control group, RIMO will have a direct effect on: a) initiating MAT sooner, b) staying on medication longer, c) reducing dropout, and d) receiving more total days of MAT.

**Aim 2: Evaluate RIMO's direct and indirect (via MAT) effects on time to relapse, opioid use, and opioid-related overdose.**

H2: RIMO will have direct and indirect (via days of MAT treatment) effects on: a) time to relapse, b) days of opioid use, and c) number of overdoses.

**Aim 3: RIMO's direct and indirect (via MAT and opioid use) effects on opioid-related fatalities, OUD symptoms, physical health, mental health and the cost of health care utilization.**

H3: RIMO will have direct and indirect (via days of MAT treatment and days of opioid use) effects on: a) opioid-related fatalities, b) opioid use disorders symptoms, c) physical health, d) mental health, and e) cost of health care utilization.

Referral Only Control. During the phase 1 pilot, we collaborated with our study partners as well as the Illinois Opioid STR partners to develop a brochure that includes a list of MAT providers in Chicago, and their location, telephone number, hours of operation, adjacent bus lines, and type of funding accepted (e.g., Medicaid). In addition, the brochure includes a range of other SUD treatment options (e.g., residential or outpatient drug-free treatment), including office-based physicians who prescribe buprenorphine or other forms of MAT. This brochure is will be given to participants in both groups at the baseline assessment. Research staff will follow a script that does not include any statements regarding motivation for treatment. At present, based on our interviews with key informants and focus group with pilot study participants, there is currently no systematic method in place for referring individuals to MAT (or other SUD treatment) either from the first responders following administration of naloxone or at the EDs following their admission for opioid-related overdose. Hence, this condition represents more than the “usual care” in the community.

Recovery Intervention and Management after Overdose (RIMO) is a version of Recovery Management Checkups (RMC) that has proven effective in 3 prior clinical trials, a quasi-experiment, and now in the randomly controlled pilot in RIMO's phase 1. For those assigned to the RIMO group, the Linkage Managers (LM) will use motivational interviewing (MI) techniques to: 1) identify the need for treatment and barriers to going, 2) discuss with patients the benefits of their decision to go to treatment, including activities they might enjoy as well as things they do not like about their alcohol/substance use, 3) provide personalized feedback to participants about the status of their condition based on responses to the assessment instruments, 4) help participants resolve ambivalence about their use and move them toward a commitment to change by accessing additional care, 5) address existing barriers to treatment (e.g., childcare, transportation), 6) schedule a treatment appointment, and 7) facilitate SUD treatment re-entry and engagement. The LM will stay in contact with the patient weekly by telephone for at least 4 weeks to ensure that patients both initiate and remain engaged in SUD treatment. This includes working with the individual and the treatment provider to minimize early discharges. Specifically, the Linkage Manager will follow-up with the treatment agency and/or the patient to see if the patient showed for the appointment. For participants who miss a dose, the LM will contact them to discuss barriers and ways to remove them. Additionally, the LM and MAT provider will coordinate information on the participant's barriers to treatment engagement (i.e., scheduling, transportation) and assist the participant in problem-solving solutions to support their treatment retention. During the first 30 days of MAT, the research team will provide transportation assistance for those in need.

For participants who refuse the referral to MAT, the LM will use motivational interviewing (MI) techniques to explore the perceived benefits and consequences of the individual's current opioid/heroin use as well as explore their motivation for treatment. Using empathy and reflection, the LM will explore the issues and barriers participants face when thinking about going to treatment. Using open-ended questions, the LM will explore not only reasons the individual opted out of the referral to MAT, but also the potential benefits of treatment. The LM will try to develop some discrepancy between where the participant is currently and where they want to be. The LM will use the MI technique of “rolling with resistance” and assure the participant that the decision is up to him/her regarding treatment - empowering the participant in the decision process and encouraging “change talk”. The LM will document the various reasons that participants cite for declining the treatment referral. Learning more about the reasons for these refusals can further inform the development or refinement of strategies for improving linkages. Our experience with other similar trials indicates that many refusals are situational or temporary in nature (e.g., illness, fatigue, sick family member) and simply re-contacting the person at a later date is, in some cases, sufficient to convert a refusal. We will routinely re-contact individuals who refuse linkage to detox or MAT to ascertain if their feelings about entering treatment have changed and continue to engage with them using MI. If the individual is not interested in MAT or other types of treatment, the LM and participant will develop an alternative action plan, which may include specific behaviors and recovery activities (e.g., carry naloxone, attend self-help, get a sponsor) to reduce or stop use.

Follow-up. The team will implement [name] follow-up procedures and conduct assessments at 3, 6, and 9 months post-randomization. This model has reliably produced over 90% follow-up rates across studies involving over 70,000 participants of diverse characteristics over follow-up periods ranging from 3 months to 19 years. Steps include: (a) contacting all participants within 24-48 hours of study intake to collect additional locator information and mailing a schedule card for the next interview, (b) recording information in an MIS, (c) assigning each case to an experienced follow-up case tracker, (d) verifying locator data, (e) conducting outreach for unverified cases and discussing them at weekly meetings, (f) mailing thank-you cards to participants and collaterals, (g) scheduling follow-up appointments, (h) mailing 3 and 6 week post-enrollment flyers, (i) implementing returned-mail procedures, (j) calling participants 6 weeks before appointment to confirm date and location (phone vs. research office), (k) conducting outreach for unconfirmed cases and reviewing

them at weekly meetings, (l) completing follow-up interviews and scheduling next appointments, and (m) implementing a no-show protocol. Participants will receive a \$25 incentive upon completion of each interview (\$100 across). Progress will be monitored with daily management reports. These procedures will help maintain participant contact for individuals in both the RIMO and referral-only groups.

**Data Editing and Quality Assurance.** When possible, computer-assisted personal interviews will be conducted. The GAIN interview conducts range checks, makes simple and complex skips, and allows immediate consistency checks. If an interview needs to be done with paper and pencil (e.g., detention, jail, and hospital), the interviewer will field edit it followed by a second edit to verify that key fields are complete, provide feedback and/or get clarification of questions, and mark any missing/bad data. The Research Manager will review inconsistent or missing data with the interviewers. When the data are keyed, the computer system will again check for range and consistency across multiple items. Weekly management reports will be used to monitor performance and error reports will be reviewed weekly until there are no major problems (or when there is a new staff person), then monthly thereafter.

**Missing data.** Participants will complete their baseline interview prior to randomization. Based on prior studies conducted by the applicants, it is expected that approximately 90% or more of the 3, 6, and 9-month post-randomization interviews will be completed. Among these completed interviews, prior studies conducted by the team indicate that less than 1% will have additional missing data on any of the core items required to test the study hypotheses. Multiple imputations will be used to replace the small amounts of missing data to allow the least biased estimate for each analysis. To further reduce potential bias, analyses will be rechecked by running them without missing data. If there are any clinically significant differences ( $d > |.2|$ ), a general latent variable framework will be used to analyze non-ignorable or systematic missing data that tests whether missing data is qualitatively different by condition.

Table 1.1 provides a schedule of events by person. We are currently planning to start recruitment immediately and for 18 to 24 months. Follow up (and RIMO) at 3, 6, and 9 months will start at month 3 and be completed between months 30 to 36 depending on how long it takes to recruit the sample. Quality assurance checks will be done until all staff are certified and then quarterly during the study. Annual data safety monitoring reports will be done annual (discussed further below) and then main findings will be started immediately upon the completion of data collection.

	Timing	Passive Referral Control	RIMO Experimental
Screening and recruitment after overdose	Up to 1 week prior to random assignment	Yes	Yes
Informed Consent and Randomization	Point of random assignment	Yes	Yes
Provide a brochure on accessing MAT and financial assistance	Point of random assignment,	Yes	Yes
Interview, urine test and record abstraction	Enrollment, 3, 6, and 9 months post enrollment	Yes	Yes
RIMO Linkage Assistance	Enrollment, 3, 6, and 9 months post enrollment	--	Yes

## **2. Primary and secondary objectives and outcome measures**

The primary outcome measure for the study is the GAIN-Quick Version 3 (GAIN-Q3). The GAIN-Q3 includes 4-6 symptom count screeners that are correlated .9 or more with the 11 to 43-symptom version in the full GAIN. It also has cut points with excellent (~90%) sensitivity, specificity, and area under the curve (AUC) relative to the full GAIN in 9 problem areas related to substance use disorders, physical health, internalizing and externalizing mental health disorders, as well as school, work, stress, HIV risk behaviors/victimization, and crime/violence. The days of use measures have been validated against the Timeline Follow-back, collateral reports, and urine and saliva tests. The GAIN-Q3 also includes summary measures for health care utilization, functional impairment, quality of life, and life satisfaction. The GAIN-Q3 includes the behavioral health screener and health care utilization measures that have been recommended by NIH's Phenx common data elements as two of the most reliable, valid, efficient, and inexpensive tools in the field. At each follow-up, the Q3 follow-up will be supplemented with a) a section on overdose and naloxone experiences, and b)

symptom counts from the OUD scale. Table 2.1 crosswalks the key independent measures and secondary outcomes from the hypotheses to their definitions, reliability, data sources, and the specific aims they address.

Table 2.1. Crosswalk of Variables, Definition, and Aims	H1	H2	H3
Experimental Assignment: Based on computer-generated urn randomization, participants will be assigned to the referral only control group or the experimental RIMO condition.	R	R	R
MAT Time to Initiation: Days from index naloxone administration to the initiation of any kind of MAT, from treatment records.	O		
Length of Staying on Medication: Days between MAT initiation and discharge, from treatment records.	O		
MAT Days: Total days of MAT over 9 months from GAIN-Q3 and treatment records.	O	M	M
Time to Relapse: Days from randomization to next subsequent use of opioids or heroin based on GAIN Q3 follow-up interviews and urine tests.		O	
Opioid Days of Use: Days of opioids and/or heroin use summed over the GAIN-Q3 follow-up interviews.		O	M
Opioid Overdose: Number of opioid-related overdose[s] summed over the GAIN-Q3 follow-up interviews.		O	
Opioid Related Fatality: Any ICD-10 cause of death related to opioid overdose (T40.1, T40.2, T40.3, T40.4, T40.6, X42, X44, X62, X64, Y12, Y14) in CDC death records.		O	
Opioid Use Disorder: The average of 11 past 90-day items on the Opioid Use Disorder Scale (11 DSM-5 symptoms) self-reported from the GAIN-Q3 follow-up interviews			O
Physical Health: The average of 5 past 90-day items on the Health Problem Screener (worried about health, pain, health kept participant from meeting responsibilities) from GAIN-Q3 follow-up interviews.			O
Mental Health: The average of the past 90-day items across the Internalizing (symptoms of depression, anxiety, trauma, suicide) or Externalizing (symptoms of attention deficit, hyperactivity, conduct, gambling) Disorder			O
Cost of Health Care Utilization: Sum of the quarterly costs of health care from the GAIN-Q3 follow-up interviews; based on the frequency of health, mental health or substance-related ED visits, hospitalizations, residential treatment, outpatient surgery, MAT, intensive outpatient, outpatient treatment days/times multiplied by their respective costs using published estimates by health economists, adjusted for inflation using the CPI.			O
Key: R=Randomization, O=Outcome, M=Mediator			

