### 4. Sample size and power calculation

We plan to recruit and randomize 350 participants over 24 months. There should be 99% or more power to determine the direct effect of RIMO on the primary outcome of time to MAT initiation (H1a) assuming a sample size of 350 patients, randomized into two groups of 175 each, interviews at 4 time points for the main analysis (baseline, and 3, 6, and 9 months post-randomization), our average completion rate of 94+% per follow-up wave, and a moderate to large effect size of  $d=3.0$ . This expected effect size was based on the natural log of the odds ratio ( $\text{Log}^e(\text{OR})=d$ ) of initiating MAT ( $\text{OR}=20.2$ ) from RIMO Pilot study ([name] et al., under review). For the other tests of direct effects, the effective n for power calculations in repeated measures analysis varies between a lower bound of the number of unique people per group ( $N=175$  people), and an upper bound of the number of people randomized plus the completed follow-up interviews or 668 observations per group ( $O=(175 \text{ people at intake} + \text{average of } 94\% \times 175 \text{ people} \times 3 \text{ follow-ups})$ ) as a function of the intra-class correlation coefficient (ICC) associated with the individual and the number of repeated measures (RM) per person ( $\text{effective } n'=O/(1+\text{ICC}(\text{RM}-1))$ ). In our prior studies, ICC of the other dependent

variables ranged from .13 to .34. Thus the effective n= range from 429 to 398 per group and be capable of detecting an effect size of  $d=0.2$  or more with 80% power for a two-tailed test of  $p<.05$  of effect sizes  $d=.2$  or more. For mediation analysis, the tests should also have 80%+ power for a 2-tailed test of  $p<.05$  and an indirect effect size of  $d=.2$  or more.

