Direct Effects of RIMO on MAT (Aim 1). Relative to the referral only control group, the direct effects of RIMO on reducing dropout and receiving more total days of MAT will be evaluated using a multilevel structural equation modeling (MSEM) with mixed effects in MPlus (version 7.4). The analysis will model observations (Level 1) nested within participants (Level 2), with participants modeled as a random factor anchored on the baseline version of the dependent variable. Randomization to RIMO will be modeled as a Level 1 predictor. We will check for the need to use models that adjust for counts or zero saturation.

Direct Effects of RIMO on Secondary Outcomes of Time to Relapse, Opioid Use and Overdose (Aim 2) and Death, OUD, Health, Mental Health, and Health Care Utilization (Aim 3). Relative to the referral only control group, the direct effects of RIMO on time to first relapse (H2) will be evaluated with a survival analysis similar to Aim 1 H1. It will be examined after the point of randomization and after each follow-up interview. The direct effects of RIMO on days of opioid use (H2), opioid overdoses (H2), opioid-related fatality (H3), symptoms of OUD (H3), physical health problems (H3), mental health symptoms (H3), and the cost of health care utilization (H3) will also be evaluated using a series of MSEM with mixed effects in MPlus modeled in the same way as above. Most of the above variables are relatively continuous, but we will check for the need to use models that adjust for counts or zero saturation. For opioid-related fatality (H3), we will define the dependent variable as dichotomous in MPlus (equivalent to using logistic regression).

Indirect Effects of RIMO (Aims 2 and 3). To evaluate indirect effects, we will determine the extent to which the direct effects of RIMO on the above dependent variables are changed by of days of MAT received (H2 & H3) and/or days of opioid use (H3) using the Preacher and colleagues framework for testing mediation in MSEM with REML in MPlus. Loss of statistical significance in the path coefficient from the intervention conditions to the other outcome variables would indicate full mediation; a reduction in the path coefficient would indicate partial mediation. Change will be evaluated using MacKinnon's joint-significance testing of the path *z*-scores with a Sobel test using a standard error based on bootstrapping and criteria of  $p < .05$  on the degree of change.

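### Both mediators are defined only as whole-follow-up totals with no stated time order, so if used as written they count days that come after the outcome

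*Combined protocol and SAP*

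**What the plan says.** Table 2.1 (Section 2) gives one definition per mediator. MAT days, mediator for H2 and H3, are "Total days of MAT over 9 months from GAIN-Q3 and treatment records". Opioid days, an outcome for H2 and a mediator for H3, are "Days of opioids and/or heroin use summed over the GAIN-Q3 follow-up interviews".

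The indirect-effects paragraph of Section 10 asks how far the direct effects are "changed by of days of MAT received (H2 & H3) and/or days of opioid use (H3". It names a multilevel mediation framework, joint significance of the paths and a bootstrapped Sobel test at p < .05. It gives no lag, no cut-off of the mediator at the time of the outcome, and no sensitivity analysis for effects running from outcome to mediator.

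Outcomes are collected throughout follow-up. In Section 1 the team will "conduct assessments at 3, 6, and 9 months post-randomization", and Table 1.1 schedules interviews, urine tests and record abstraction at "Enrollment, 3, 6, and 9 months post enrollment". Section 4 counts "interviews at 4 time points for the main analysis (baseline, and 3, 6, and 9 months post-randomization". Section 10 sets the level of analysis: "The analysis will model observations (Level 1) nested within participants (Level 2". OUD symptoms, physical health and mental health refer to the past 90 days. Relapse is "Days from randomization to next subsequent use of opioids or heroin based on GAIN Q3 follow-up interviews and urine tests". Opioid days, overdoses and health care cost are sums over follow-up.

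**The concern.** A mediator has to precede the outcome it is meant to explain. A 9-month total does not precede a 3-month symptom score or an early relapse.

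The design also makes feedback from outcome to mediator plausible. RIMO linkage contact recurs at 3, 6 and 9 months, need for treatment is recorded at each meeting (Section 8), and Section 10 plans to examine MAT initiation after each checkup. Use or overdose in one quarter may therefore change MAT in the next, and a 9-month total counts that later MAT as if it had come first.

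The indirect effects are stated hypotheses under Aims 2 and 3. The joint-significance test needs both paths. The pilot saw 11.2 against 0.76 days of MAT, so the path from RIMO to MAT is likely to pass, and the conclusion then turns on the path from MAT to outcome, where the order is not fixed.

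**Working it through.** **1. The plan's own figure.** Section 4 claims 80%+ power for an indirect effect of d = .2. It gives neither the RIMO-to-mediator path nor the mediator-to-outcome path, so the figure cannot be reproduced.

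**2. Timing.** The share of a 9-month window that falls after an outcome at month t is (9 − t)/9:
- 3 months: 6/9 = 67%
- 6 months: 3/9 = 33%
- 9 months: 0/9 = 0%

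For time to relapse, all MAT after the event is included. For outcomes that are themselves sums (opioid days, overdoses, cost), the two windows coincide and no order is set.

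**3. Simulation, total on total.** From Section 4: 175 per arm. Assumed: three quarters; MAT in a quarter for 45% (RIMO) and 15% (control); 0.15 overdoses per person-quarter; no effect of MAT on overdose; an overdose shifts the chance of MAT in the next quarter by the amount shown. There were 1,000 trials per setting in the basic set-up. Models:
- Path a: total MAT days = a0 + a·arm
- Path b: total overdoses = b0 + b·(total MAT days) + c·arm
- False mediation: both a and b significant at p < .05

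| Shift in chance of MAT after overdose | False mediation with 9-month totals |
|---|---|
| −10 points | about 12% |
| 0 | about 5% |
| +10 points | about 16% |
| +20 points | about 38% |
| +30 points | about 66% |

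Repeat runs, including one with a different distribution of MAT days, gave 61% to 71% at +30. At positive shifts almost none of the false results had a protective sign. At −10 nearly all pointed towards benefit. If half of participants carry their MAT status into the next quarter, the inflation shrinks to 7–23%. At 80% carry-over it is about nominal. If only the RIMO arm reacts to an overdose, the rates are 12% at +20 and 23% at +30.

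**4. Simulation, total on a single wave.** Assumed: n = 350, 2,000 runs, continuous use and MAT, wave correlation .34 (the upper ICC in Section 4), no MAT effect on use, and use lowering next-quarter MAT by 0.1 to 0.3 SD. When RIMO raises MAT by 0.2 SD per quarter, the 9-month total gave false mediation in 22–72% of runs for the 3-month outcome and 18–69% for the 6-month outcome. When RIMO raises MAT by 0.5 SD, the figures were 32–99% and 25–97%. With no reverse effect the rate was 3–5%. These false effects point to benefit. They apply only if the total is set against each wave separately.

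**5. Alternatives.** In the overdose set-up, mediators by wave that never run past the outcome held false mediation at 3–7%. Power was then compared when MAT halves overdoses in the quarter it is received, across degrees of carry-over:

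| Mediator | Power |
|---|---|
| 9-month total | 32–73% |
| Same wave | 81–83% |
| Strict lag | 6–49% |

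All of these are single-level or person-clustered regressions, not the planned multilevel model.

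**The case against.** **The plan may intend MAT days by wave.** Section 10 tests total MAT days in a model of repeated observations anchored on a baseline value. One 9-month total can be neither a repeated observation nor have a matching baseline version. A reader might infer that the plan definitely sets the total against every wave, so that 67% and 33% describe the planned analysis. The documents do not say that, and under a per-wave reading those shares disappear. This stands, and it makes the point conditional. But no per-wave mediator is defined anywhere, and Table 2.1 holds the only definition.

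**A person-constant mediator acts on the person's average over waves, and several outcomes are sums.** This is correct: for those outcomes the shares do not apply. The windows then overlap fully, which is the case in step 3, so the lack of order remains.

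**The large rates are not false successes.** A reader might infer that the plan will declare a false benefit in up to two thirds of trials. The documents do not support this. They give no effect of overdose on later MAT. The 66% belongs to a positive shift, whose false results link MAT with more overdoses, against H2. Step 4 does give large rates towards benefit, but on assumed reverse effects and one reading of the model.

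**Lagging everything would be worse.** It drops first-quarter outcomes, although RIMO contact is concentrated in the first weeks, and it loses much power if MAT protects mainly while taken. This stands against a lagged model as the only test.

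**Mediation is secondary.** True, but Aims 2 and 3 state indirect effects and Section 4 claims power for them.

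**Conclusion.** The gap is in the text: each mediator has one definition, a whole-follow-up total, and nothing fixes its order relative to the outcome. The bias is conditional on those totals being used as written and on use or overdose changing later MAT. Under the assumptions of step 3 the false-mediation rate lies between about 5% and 66%. It is close to nominal when MAT status largely persists, mostly against H2 for positive shifts, and about 12% towards false benefit for a shift of −10 points. The rates in step 4 can be higher, but they need the total to be entered wave by wave. No single figure should be quoted as the error rate of this trial. The time-to-relapse analysis is the clearest case, because it does not depend on how the multilevel model is read. The primary analysis and all direct-effect tests are unaffected.

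**What to change.** In Table 2.1 and Section 10, for the indirect-effect tests:
- Define MAT days and opioid days by wave, counting only days up to the interview at which the outcome is measured, and adjust for the outcome at the previous wave (baseline for the 3-month outcome). Use outcomes that are defined as sums by wave in these tests too.
- For time to relapse, count MAT days only up to the relapse date. Enter them as a time-dependent covariate, since a plain count grows with the time to relapse itself.
- As a sensitivity analysis for reverse effects, add a lagged model: mediator up to the previous interview, outcome in the next quarter. For H3, use MAT in months 0–3, opioid days in months 4–6 and the outcome at 9 months.
- Keep the 9-month totals for the direct-effect tests.

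The cost is wording plus re-cutting data already scheduled at 3, 6 and 9 months. Treatment records, which already supply MAT initiation and discharge, would be needed to date MAT relative to relapse. The downside is that a same-wave mediator and outcome share a 90-day window, so order within the quarter stays unproven and should be stated as a limitation.

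### Total MAT days over 9 months is tested as a mediator of opioid-related death, but death shortens MAT days, so the MAT-to-death path is biased toward protection

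*Combined protocol and SAP*

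**What the plan says.** Hypothesis H3 (Section 1, Aim 3) states: "RIMO will have direct and indirect (via days of MAT treatment and days of opioid use) effects on: a) opioid-related fatalities".

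Table 2.1 (Section 2) defines the mediator MAT Days as "Total days of MAT over 9 months from GAIN-Q3 and treatment records" and codes it as a mediator for H2 and H3. The fatality outcome is "Any ICD-10 cause of death related to opioid overdose", taken from CDC death records, with no time window given. Opioid days of use, the other H3 mediator, is a sum over the follow-up interviews.

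Section 10 gives the outcome model: "For opioid-related fatality (H3), we will define the dependent variable as dichotomous in MPlus (equivalent to using logistic regression"). It then asks how far "the direct effects of RIMO on the above dependent variables are changed by of days of MAT received", and for H3 also by days of opioid use. Fatality is among those dependent variables. Mediation is judged by loss of significance or reduction of the RIMO path, and by joint significance "with a Sobel test using a standard error based on bootstrapping and criteria of" p < .05.

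Nothing divides MAT days by days alive, measures MAT before the period at risk, or says how days after death are counted. Section 10 mentions death only as a reason for censoring in the survival analyses. The missing-data text does not mention deceased participants.

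**The concern.** A mediator must come before the outcome it explains. A 9-month total does not do so for a death inside those 9 months. Someone who dies on day 60 can have at most 60 MAT days, while a survivor can have about 270. Participants who died will therefore show fewer MAT days than survivors even if MAT does nothing, and a logistic model without time of death reads that gap as protection. The RIMO direct path then moves the other way to compensate.

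At stake is the H3 decomposition for fatality. The plan could report a protective indirect path through MAT, and an apparently adverse direct path of RIMO, when both come only from the shortening of MAT time by death.

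**Working it through.** The plan states no figure for this analysis, so there is nothing to reproduce. The check is whether the planned analysis returns a null result when the truth is null.

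**Inputs from the documents.** 350 participants, 175 per group (Section 4); mediator and outcome definitions (Table 2.1); dichotomous outcome, joint significance with a Sobel test, two-sided .05 (Section 10).

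**Assumed inputs.** Opioid deaths within 9 months, MAT initiation and length of stay. Deaths are spread uniformly over 270 days and are independent of MAT and of arm, so the true odds ratio is 1.0 for both MAT and RIMO.

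**Model.** One row per person: logit P(death) = b0 + c'·RIMO + b·(MAT days/30), with MAT days stopped at death. The a-path is the difference in mean MAT days between arms. Joint significance requires both a and b to be significant. The Sobel statistic is z = a·b / √(a²·SE_b² + b²·SE_a²), a delta-method version rather than the planned bootstrap.

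**Step 1: size of the bias.** Three MAT patterns, very large sample, 5% deaths:

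| Survivors' mean MAT days, control / RIMO | Mean MAT days of those who died, control / RIMO | OR per 30 MAT days | RIMO direct OR |
|---|---|---|---|
| 7.7 / 114.2 (pilot-like) | 4.2 / 65.7 | 0.859 | 1.517 |
| 33.0 / 72.8 | 16.7 / 42.4 | 0.862 | 1.164 |
| 67.7 / 116.2 | 34.9 / 68.0 | 0.850 | 1.261 |

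In the RIMO arm, those who died have 65.7/114.2 = 58%, 42.4/72.8 = 58% and 68.0/116.2 = 59% of the survivors' MAT days, from truncation alone.

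A separate set of simulations, with initiation of 30% vs 60% or 50% vs 80% and a mean stay of 120 or 200 days, gives an OR of about 0.84-0.86 and a RIMO direct OR of about 1.15-1.27.

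**Step 2: is truncation the cause?** In the three patterns above, using MAT days not cut by death gives an OR of 0.998-1.000. A month-3 landmark (MAT days to day 90, deaths after day 90 among those alive) gives 0.991-1.005. With either, false protective mediation by joint significance at N = 350 is at most about 2.3%, against a nominal 2.5% per tail.

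**Step 3: false mediation at N = 350**, under the initiation and stay assumptions of the separate set:

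| Deaths assumed | Joint significance alone | Joint significance plus Sobel |
|---|---|---|
| 2% (0.02 × 350 = 7) | 0-3% | 0-0.4% |
| 4% (0.04 × 350 = 14) | 0.3-25% | 0.1-11% |
| 8% (0.08 × 350 = 28) | 15-65% | 4-46% |

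The upper ends come from high initiation combined with long stay.

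**Step 4: the second mediator.** Days of opioid use are also cut short by death. Those who died accrue fewer opioid days, so opioid use looks less harmful than it is. That bias runs against H3.

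**The case against.** A reader might infer that the trial would wrongly announce that RIMO prevents opioid deaths through MAT. The documents do not support that.

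- **Total effect.** The randomized comparison of fatality does not involve MAT days and is not biased.
- **Decision rule.** Section 10 identifies mediation by a RIMO path that loses significance or shrinks. Under the null, adding MAT days moves that path on average away from 1. Joint significance alone also overstates the error rate, because the plan adds a Sobel test. In a further simulation (2,000 runs per cell), also requiring a protective RIMO path that shrinks left false mediation at 0-0.1%, 0-2.5% and 1.0-15% at 2%, 4% and 8% deaths. A false joint test together with a significant protective total effect occurred in at most 1.0% of runs in any cell.
- **Few deaths.** At 7 deaths a false finding is rare.
- **Opioid days.** A reader might take the same truncation as a second source of false support for H3. It works in the opposite direction.
- **Model form and window.** Section 10 nests observations within participants, while the simulations use one row per person with MAT days as the only mediator. The fatality window is unstated, and deaths after month 9 would dilute the bias.

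These points stand and limit the consequence. They do not remove the bias in the estimate. At 7 deaths the median OR is still 0.84; low power only makes it less often significant. Quarterly rows would not help without a lag: unlagged quarterly MAT days gave an OR of 0.64-0.69 per 30 days in a null simulation, and a one-quarter lag gave about 1.01. Imputing MAT days after death would shrink the truncation, but those values have no meaning and the plan does not say this is intended.

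**Conclusion.** The concern holds in a limited form. For opioid-related deaths within the 9 months, the planned MAT-to-death path is biased toward protection by the construction of the mediator: about OR 0.84-0.86 per 30 MAT days when the truth is 1.0. The RIMO direct path is pushed to about 1.15-1.27, and to 1.52 under a pilot-like contrast in MAT days.

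How often this yields a false mediation finding depends on inputs the documents do not give. It is negligible near 2% deaths and material only when deaths and retention are both high. The rates rest on uniform death times, one row per person, a single mediator and a delta-method Sobel test.

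The affected result is one direct/indirect split for one secondary outcome. The primary outcome and the randomized comparison of fatality are untouched.

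**What to change.** In Section 10, exclude opioid-related fatality from the indirect-effect tests and keep the randomized comparison of RIMO with control. Amend H3 to match, and state the time window for fatality in Table 2.1.

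If the link between MAT and death is still wanted, use only MAT exposure that precedes the risk period. Either of these would do:

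- a landmark analysis: MAT days to month 3, then deaths after month 3 among those alive;
- a Cox model for opioid-related death with time-dependent MAT status.

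Report it as an exploratory, non-randomized association between MAT and death, not as an indirect effect of RIMO.

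The cost is a wording change. Treatment records and death records are already planned sources, and Cox regression is already in the plan. One low-powered secondary mediation test is dropped or becomes exploratory. A landmark leaves out deaths before month 3, and either replacement will have few events.
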